15.1.1 All Adverse Events

Adverse events will be summarized by worst severity (according to NCI-CTCAE version 5.0), in alphabetical order by MedDRA PT as event category and MedDRA primary system organ class (SOC) body term as Body System category, using MedDRA version 23.0 or later.

In case a participant has events with missing and non-missing grades, the maximum of the non-missing grades will be displayed. No imputation of missing grades will be performed.

Incomplete AE-related dates will be handled as specified in Section 9.8.

The following tables will be created, by treatment group:

- Overall summary of AEs: it will include the frequency (number and percentage) of participants with each of the following:
 - TEAEs
 - TEAEs with NCI-CTCAE Grade ≥ 3 , Grade ≥ 4
 - Related TEAEs
 - Related TEAEs with NCI-CTCAE Grade ≥ 3 , Grade ≥ 4
 - TEAEs leading to permanent treatment discontinuation
 - Related TEAEs leading to permanent treatment discontinuation
 - Serious TEAEs
 - Related Serious TEAEs
 - TEAEs leading to death
 - Related TEAEs leading to death

- TEAEs by SOC and PT
- TEAEs by SOC and PT and worst grade
- Treatment related TEAEs by SOC and PT
- Treatment related TEAEs by SOC and PT and worst grade
- TEAEs leading to death by SOC and PT
- Related TEAEs leading to death by SOC and PT
- TEAEs excluding SAEs, with frequency $\geq 5\%$ in any treatment arm by SOC and PT
- TEAEs by age subgroup, as defined in Section 8.2, by SOC and PT
- TEAEs by gender subgroup, as defined in Section 8.2, by SOC and PT.

15.1.2 Adverse Events Leading to Discontinuation of Study Treatment

TEAEs leading to permanent discontinuation of study drug are those events recorded as “Drug withdrawal” on the AE pages of the eCRF.

The frequency (number and percentage) of participants with each of the following will be presented for TEAEs leading to permanent discontinuation of each study drug by treatment group:

- TEAEs leading to study treatment discontinuation by SOC and PT
- Related TEAEs leading to study treatment discontinuation by SOC and PT

15.2 Deaths, Other Serious Adverse Events, and Other Significant Adverse Events

15.2.1 Deaths

All deaths will be tabulated based on information from the “Death” eCRF page, summarizing the following information:

- Number of Deaths
- Number of Deaths within 30 days after last dose of study treatment
- Primary Reason of Death, among:
 - Progressive disease and/or other disease related condition
 - Event unrelated to study treatment
 - Unknown

In addition, date and cause of death will be provided in individual participant data listing together with selected dosing information (date of first and last administration and number of doses).

This listing will include:

- AEs with fatal outcome (list preferred terms of AEs with outcome=fatal)
- Flag for death within 30 days of last study treatment

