- If the ECG QTc interval (corrected by Fridericia's formula) increases to > 480 msec, an immediate investigation into potential drug causes should be performed, and the study intervention temporarily withheld. If the participant is not on any known drugs to prolong QTc, then kidney function should be reviewed and also a potential drug interaction should be considered. The contraindicated drug list should be reviewed for study contraindicated medications (e.g., aldehyde oxidase inhibitors) and the offending drug discontinued unless no alternatives are available for management of the participant. If the QTc returns to the participant's Baseline or the prolongation is assessed as related to the underlying SARS-CoV-2 infection of the perimyocardium, in the opinion of the Investigator, the study intervention may be restarted any time before Day 15.

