10.4.4 Safety Analysis

Adverse events will be coded according to the Medical Dictionary for Regulatory Activities (MedDRA). The number and percentage of participants experiencing 1 or more treatment-emergent adverse events (TEAEs) will be summarized according to MedDRA system organ classes and preferred terms by treatment group, relationship to study intervention, and severity.

Deaths, SAEs, AESIs, TEAEs leading to treatment discontinuation, and TEAEs leading to treatment interruption will be summarized by treatment group.

Summary statistics will be used to present observed values and changes from Baseline in vital signs, ECG parameters, and abnormal laboratory parameters.

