Previous and concomitant treatments will be summarized separately by number and percentage of participants from the “Concomitant medications” eCRF page. Anatomical Therapeutic Chemical classification (ATC) 2nd level and preferred term will be tabulated as given from the WHO-DD dictionary most current version. If any medication is classified into multiple ATC classes, the medication will be summarized separately under each of these ATC classes. The summary tables will be sorted by decreasing frequency of drug class and decreasing frequency of drug name in a given drug class in the total column. In case of equal frequency regarding drug class (respectively drug name), alphabetical order will be used. In case any specific medication does not have an ATC classification level 2 coded term, it will be summarized under “UNCODED ATC classification” category. Each participant will only be counted once per medication, even if he/she received the same medication at different times.

All medications (prior, and concomitant) will be listed.

All **concurrent procedures**, collected in the “Related Procedures” eCRF page, will be coded using MedDRA version 23.0 or higher and reported in listings.

13 Study Treatment: Compliance and Exposure

The following analyses will be performed based on the ITT/SAF analysis set by treatment group.

All dosing calculations and summaries will be based on “Exposure” eCRF page. Each participant is expected to be treated with the drug assigned by the randomization system for 14 consecutive days, twice per day.

In case of discharge from the hospital before the end of treatment period, the participant will be instructed to take the study treatment at home and a diary card will be handled to collect daily dosing information.

In case the start date is missing or incomplete, it is assumed that the first dose of study treatment is given at the randomization date.

Duration of exposure to study drug (days) = (end date/time – date/time of first dose of study drug), where end date/time is the date/time of last dose of study drug.

Dose administered at each administration will be derived as follows:

- Participants randomized to M5049 50 mg = number of tablets administered * 12.5 mg
- Participants randomized to M5049 100 mg = number of tablets administered * 25 mg

Cumulative dose is the sum of all doses administered.

Compliance will be derived using information from ‘Drug accountability’ eCRF page.

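### SAP 15.2.1 has no treatment-related reason for death, and the interruption summary promised in Protocol 10.4.4 has no specified SAP table

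*SAP*

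**What the plan says.** **Deaths.** SAP 15.2.1 tabulates deaths from the Death eCRF page. It gives three primary reasons: "Progressive disease and/or other disease related condition", "Event unrelated to study treatment", and unknown. The accompanying listing gives date and cause of death and includes "AEs with fatal outcome (list preferred terms of AEs with outcome=fatal". In SAP 15.1.1, related fatal TEAEs appear as a row of the overall AE summary and again as a separate table, "Related TEAEs leading to death by SOC and PT".

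**Interruptions.** Protocol 10.4.4 lists deaths, SAEs, AESIs, TEAEs leading to discontinuation, "and TEAEs leading to treatment interruption will be summarized by treatment group". The action-taken outputs in SAP 15.1.1 and 15.1.2 concern permanent discontinuation only. SAP 15.1.2 ties them to one eCRF entry ("TEAEs leading to permanent discontinuation of study drug are those events recorded as" a drug withdrawal). SAP Section 7, which records departures from the protocol's analyses, mentions only the handling of stratification factors.

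**The concern.** A list of reasons for death that offers an unrelated event but no related one cannot hold a death that the investigator attributes to study drug. Safety against placebo is a primary objective (Protocol 3.2), and a reader of the report would expect the death table and the fatal-TEAE tables to agree.

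The missing interruption summary matters because Protocol 8.1 foresees holds followed by restart. For Grade 3 transaminases the study intervention is to be withheld and may be restarted. For QTcF above 480 msec the protocol calls for an investigation "and the study intervention temporarily withheld", also with possible restart. A participant who is held, restarts and completes the course will not appear in a table of permanent discontinuations. The protocol treats interruption as an outcome to be reported separately by arm, and the SAP gives it no definition, eCRF value or table.

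**Working it through.** No sample size, power or event count is involved. The check compares what the protocol requires, what the SAP lists and what data are collected.

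**1. Can the death table hold a treatment-related death?**
- Disease-related condition: no, because the attribution is to the drug.
- Event unrelated to study treatment: no, by definition.
- Unknown: no, because the reason is stated.

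Result: 0 of 3 categories fit.

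**2. Do other outputs hold it?** Yes.
- SAP 15.1.1 has 2 dedicated outputs, the overall-summary row and the SOC/PT table.
- SAP 15.2.2 adds related serious TEAEs by SOC and PT.
- SAP 9.7 runs the on-treatment period to last contact or death, so these tables cover the whole of follow-up.

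**3. Can the sources disagree?** The death table uses the Death page and the TEAE tables use the Adverse Event page. Under SAP 15.1 an event with missing relationship counts as related. A fatal event with missing relationship would therefore enter the related fatal tables, while the same death could be shown as unrelated or unknown in 15.2.1. The SAP gives no reconciliation rule.

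**4. Interruption outputs: required against specified.**

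| Item | Protocol 10.4.4 | SAP 15.1.1 / 15.1.2 |
|---|---|---|
| TEAEs leading to discontinuation | required by arm | specified: summary rows and SOC/PT tables, all and related |
| TEAEs leading to interruption | required by arm | none |

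Result: 0 specified against 1 required, with no entry in SAP Section 7.

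**5. Are the data there?** Yes. Protocol 7.3 records dates of intervention delays in the eCRF, and Protocol 9.3.6.1 records the action taken for each AE.

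**The case against.** The strongest reply is that little harm would go unseen, and most of that reply stands.

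- **Deaths.** A reader might infer that treatment-related deaths have no place in the safety outputs. The documents do not support that, because SAP 15.1.1 and 15.2.2 tabulate them and the death listing shows the fatal preferred terms. The Death eCRF page is also not available to us, so whether it offers a related option is unknown, and disagreement between the tables is a possibility rather than a certainty.
- **Toxicities behind the holds.** A reader might infer that a dose-limiting toxicity rate is understated. Neither document defines such a rate. SAP 15.3 gives shifts to worst CTCAE grade and counts by grade, with ALT and AST gradable under Appendix 1. SAP 15.5 has a QTcF category above 480 ms, the same threshold as the hold rule, and uses unscheduled ECGs for notable changes. Both are tabulated whether or not dosing was held.
- **Exposure.** SAP Section 13 computes duration from first to last dose ("where end date/time is the date/time of last dose of study drug"), so a reader might infer that exposure is overstated when dosing is held. That measure is calendar duration and is labelled as such. The same section reports cumulative dose as the sum of doses actually given, plus compliance against 112 planned tablets. As an illustration, a 3-day hold removes 3 × 8 = 24 tablets, leaving 112 − 24 = 88, and 88/112 = 79%. The shortfall shows in cumulative dose. It shows in compliance too if returned tablets are counted.
- **Removal.** A reader might infer that the SAP deliberately dropped the interruption summary. SAP 6.3 says generally that the analyses identified in the protocol will be performed, so the output is unspecified rather than expressly removed. The primary safety endpoint in Protocol 3.2 names discontinuation, not interruption, and the Protocol 10.4.4 summary covers all TEAEs leading to interruption, not only those attributed to the drug.

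What the reply does not answer is narrower. The death categories as listed cannot classify a related death, and the general sentence in SAP 6.3 supplies no interruption table, definition or eCRF value.

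**Conclusion.** Two alignment defects stand, and both should be corrected.

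1. None of the three reasons for death in SAP 15.2.1 can correctly hold a treatment-related death, and the table could differ from the fatal-TEAE tables in SAP 15.1.1.
2. One summary required by Protocol 10.4.4 has no specified SAP output, and SAP Section 7 does not declare this. The underlying events remain visible in general TEAE, laboratory and ECG outputs. What is lost is the by-arm display of events that led to a hold.

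The first conclusion takes the SAP list as complete. If the Death page already offers a related option, the defect lies in the SAP wording alone. The documents give no rate of treatment-related deaths or of holds, so no participant count is attached to either point, and neither conclusion depends on one.

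**What to change.** - **SAP 15.2.1:** add a category for an event related to study treatment, and add it to the Death eCRF page if absent there. State how the table will be reconciled with the related fatal TEAE outputs in SAP 15.1.1, including fatal events with missing relationship.
- **SAP 15.1.1 and 15.1.2:** add TEAEs leading to treatment interruption, all and related, by treatment group, to the overall summary and by SOC and PT. Name the AE action-taken value that identifies them. If the sponsor does not intend this output, SAP Section 7 should declare and justify the departure from Protocol 10.4.4.

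The cost is SAP wording and a few tables, preferably settled before database lock and unblinding. The interruption summaries need no new data, and no clinical rule changes. The only possible data-collection change is one response option on the Death page.

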15.2.2 Serious Adverse Events

The following overall frequency tables will be prepared for serious treatment-emergent adverse events (SAEs):

- Incidence of serious TEAEs by SOC and PT
- Incidence of related serious TEAEs by SOC and PT

The listings of treatment - emergent SAEs will also be provided with the relevant information.

15.2.3 Other Significant Adverse Events

Adverse events of special interest will be identified on the 'Adverse Event' eCRF page and using Standardized MedDRA queries.

The frequency (number and percentage) of participants with each of the following treatment emergent adverse event of special interest (AESI) will be presented by treatment group:

- Infections, defined as any Common Terminology Criteria for Adverse Events (CTCAE) Grade ≥ 3 or serious adverse events (SAEs) of infection and opportunistic infection;
- Seizure, defined as any type of seizures/epilepsy of any grade or its consequences;
- Serotonin syndrome and its spectrum of symptoms;
- Clinically significant arrhythmias.

All AESIs will be flagged in adverse event listing.

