8.1 Temporary or Permanent Discontinuation of the Study Intervention for Toxicity

Any new clinically relevant finding is reported as an AE graded according to Common Terminology Criteria for Adverse Events (CTCAE) Version 5.0.

Participants who have their study intervention held for suspected drug toxicity, may have the study intervention restarted with approval of the Sponsor if the potential benefit of the study intervention outweighs the risk of the toxicity. More specifically, if a clinically significant finding is identified after enrollment, the Investigator or qualified designee will determine if the participant can continue on the study intervention and if any change in participant management is needed in discussion with the Medical Monitor and Sponsor.

The study intervention may not be restarted if any SAE, clinically significant AE, persistent Grade 4 laboratory abnormality, intercurrent illness, or other medical condition occurs indicating to the Investigator that continued participation is not in the best interest of the participant.

- The study intervention will not be restarted if the following occurs: serious infection other than COVID-19, seizure, clinically significant arrhythmia, or serotonin syndrome.
- The study intervention should be withheld if the participant develops Grade 3 liver function tests (i.e., an increase in transaminases [ALT or AST] > 5.0 to $20.0 \times$ ULN if Baseline was normal or > 5.0 to $20.0 \times$ Baseline if Baseline was abnormal regardless of the participants bilirubin level). If the ALT and AST do not immediately trend to the participant's Baseline values within 24 hours, the study intervention must be held until the liver function tests return to the participant's Baseline values. If the ALT and AST return to the participant's Baseline values before Day 15, the study intervention may be restarted.
- For participants whose eGFR < 40 mL/min/1.73 m² for 24 hours, experience a Grade 3 increase in serum creatinine ($> 3.0 \times$ Baseline or > 3.0 to $6.0 \times$ ULN) for 24 hours or who develop Acute Kidney Injury (requiring hemodialysis), the study intervention must be permanently discontinued.

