Hospital re-admissions (if the participant was first discharged within the 60-day study period) should be reported as SAEs (unless the admission is elective). Specifically, hospital re-admission will be considered as a COVID-19 relapse if the participant is re-admitted due to worsening oxygenation and either a positive result of any respiratory pathogen test or worsening lesions on chest imaging.

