9.3 Adverse Events and Serious Adverse Events

9.3.1 Definition of an Adverse Event

An AE means any untoward medical occurrence associated with the use of an intervention in humans, whether or not considered intervention-related. An AE can therefore be any unfavorable and unintended sign (including an abnormal laboratory finding), symptom, or disease temporally associated with the use of the study intervention.

Any medical condition that is present at the time that the participant is screened will be considered as Baseline and not reported as an AE. However, if the severity of any pre-existing medical condition increases, it should be recorded as an AE.

Given the nature of severity of the underlying illness, participants will have many symptoms and abnormalities in vitals and laboratory. All clinically important events will be captured as AEs in this study.

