9.3.4.1 Infection

[figure not shown]
Any CTCAE Grade ≥ 3 or SAEs of infection and opportunistic infection will be considered an AESI.

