9.3.6.1 Investigators Reporting of Adverse Events

Information on all AEs should be recorded on the appropriate eCRF. All clearly related signs, symptoms, and results of diagnostic procedures performed because of an AE should be grouped

together and recorded as a single diagnosis. If the AE is a laboratory abnormality that is part of a clinical condition or syndrome, it should be recorded as the syndrome or diagnosis rather than the individual laboratory abnormality. Each AE will also be described in terms of duration (start and stop date), severity, association with the study intervention, action(s) taken, and outcome.

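### The infection AESI row counts COVID-19 events and new infections together, so a between-arm difference in new infections can be diluted, masked, reversed or inflated

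*SAP*

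**What the plan says.** The incidence of AESIs from Day 1 through Day 60 is a primary safety endpoint (Protocol 3.1 and 3.2). Protocol 9.3.4.1 defines the infection AESI: "Any CTCAE Grade ≥ 3 or SAEs of infection and opportunistic infection will be considered an AESI". SAP 15.2.3 carries this into the analysis as "Infections, defined as any Common Terminology Criteria for Adverse Events (CTCAE) Grade ≥ 3 or serious adverse events (SAEs) of infection and opportunistic infection" and reports the number and percentage of participants by arm. It identifies AESIs from the adverse event eCRF page and from standardized MedDRA queries, which it does not name. Events count as treatment-emergent up to last contact or death (SAP 9.7).

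The protocol does set COVID-19 apart in one place. Section 8.1 lists the events after which study drug is not restarted: "serious infection other than COVID-19, seizure, clinically significant arrhythmia, or serotonin syndrome". These are the same four topics as the AESIs, but here with a COVID-19 qualifier on infection.

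The adverse event rules do not exempt the disease under study. Protocol 9.3.1 treats conditions present at screening as baseline, but "if the severity of any pre-existing medical condition increases, it should be recorded as an AE". Section 9.3.6.1 asks for a diagnosis rather than its components: "All clearly related signs, symptoms, and results of diagnostic procedures performed because of an AE should be grouped" into a single entry. Prolonged hospitalization and re-hospitalization make an event serious (9.3.2), and non-elective readmission is reported as an SAE (9.1.3.2).

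**The concern.** Reducing COVID-19 worsening is the effect the trial hopes to see. An excess of other serious or opportunistic infections is a harm that an infection AESI for an immunomodulator would be expected to show. If both enter one count, the row can move for either reason, and a reader cannot tell which. A drug that lessens COVID-19 progression but causes secondary infections could show no excess. A drug that worsens COVID-19 could appear to cause new infections. With about 50 participants per arm and a descriptive safety analysis, the meaning of each row matters more than any test on it.

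**Working it through.** The plan states no expected AESI rate, so there is no figure of its own to reproduce. The check has two parts: whether COVID-19 events can reach the row, and what happens if they do.

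**Route into the row.** Worsening of the baseline disease is an adverse event (Protocol 9.3.1). It is recorded as a diagnosis (9.3.6.1). It is serious if it prolongs the stay or leads to readmission (9.3.2, 9.1.3.2). If that diagnosis is an infection term, it meets the AESI definition. If it is recorded as, say, respiratory failure, it need not. The route is open, but the share of events that take it is unknown.

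**Inputs.** Planned size is 15 + 135 = 150, allocated 1:1:1 (Protocol 4.1), so 150 / 3 = 50 per arm. The remaining inputs are assumptions:
- *i*, risk of a new infection meeting the AESI criteria: 4% placebo, 10% active. Alone this gives a difference of +6.0 points, a risk ratio (RR) of 2.5, and 2 versus 5 participants expected.
- *c*, risk of COVID-19 worsening that is recorded as a qualifying infection: varied.
- The two are independent within an arm, so the combined risk is p = 1 − (1 − c)(1 − i).

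For example, with c = 20% in both arms, placebo is 1 − 0.80 × 0.96 = 23.2% and active is 1 − 0.80 × 0.90 = 28.0%. With c = 12% on active, active is 1 − 0.88 × 0.90 = 20.8%.

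| c, placebo vs active | Row, placebo | Row, active | Difference (points) | RR |
|---|---|---|---|---|
| 0% vs 0% | 4.0% | 10.0% | +6.0 | 2.50 |
| 10% vs 10% | 13.6% | 19.0% | +5.4 | 1.40 |
| 20% vs 20% | 23.2% | 28.0% | +4.8 | 1.21 |
| 30% vs 30% | 32.8% | 37.0% | +4.2 | 1.13 |
| 20% vs 15% | 23.2% | 23.5% | +0.3 | 1.01 |
| 20% vs 12% | 23.2% | 20.8% | −2.4 | 0.90 |
| 20% vs 25% | 23.2% | 32.5% | +9.3 | 1.40 |

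Equal worsening only dilutes. Masking or reversal needs the drug to reduce worsening. If the drug increases worsening, the absolute excess is overstated.

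**Break-even.** The difference is zero when c on active = 1 − (1 − c on placebo) × 0.96 / 0.90. That is 14.7% against 20% on placebo (a 27% relative reduction) and 25.3% against 30% (16%). With a larger signal of 5% versus 15%, break-even against 20% falls to 10.6%, and at 10% worsening on placebo no active rate reverses the sign.

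**Sensitivity to overlap.** If no participant has both kinds of event, risks add. Equal 20% worsening gives 24% versus 30% (+6 points, RR 1.25), and 20% versus 12% gives 24% versus 22% (−2 points, RR 0.92). The pattern is the same, but without overlap equal worsening leaves the absolute difference unchanged.

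**Precision.** SE = √[p₁(1 − p₁)/50 + p₂(1 − p₂)/50]. For 4% versus 10% it is 5.1 points. For 23.2% versus 28.0% it is 8.7 points. As a gauge only, since no test of AESIs is planned, two-sided 5% power falls from 0.22 to 0.08.

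**The case against.** **The information is available elsewhere.** SAP 15.1.1 and 15.2.2 tabulate adverse events and serious events by SOC and preferred term, and AESIs are flagged in the listing. COVID-19 worsening also appears in the clinical status, ventilation, relapse, re-hospitalization and cause-of-death summaries. With a handful of non-COVID events, a reader could separate them by hand. This largely stands: what is missing is an aggregate, not the data. But participants are counted once per preferred term (SAP 15.1), so term counts do not add up to participants with a non-COVID infection, and choosing terms after unblinding would be post hoc.

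**Including COVID-19 may be intended.** Protocol 2.1 and 4.2 place dosing after the early antiviral response, so as not to impair control of the virus. Worse SARS-CoV-2 infection is thus itself a plausible harm, and Section 8.1 is a restart rule, not an AESI definition. A reader might infer that the qualifier was dropped from the AESI by mistake; the text does not show that. The risk section is redacted and a figure is missing next to the definition in 9.3.4.1, so I do not rest the point on a stated risk. This is a reason to keep the combined row.

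**The effect is hypothetical.** It is. All rates are assumed, and even a clean comparison of 4% versus 10% would be hard to detect at 50 per arm.

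**Conclusion.** The point holds as a matter of interpretability. The plan as written can put the disease under study and new infections into one primary-safety count, with no planned participant-level count of infections other than COVID-19. Under the assumed 4% versus 10%, the RR shown could be about 1.2 with equal 20% worsening, or about 0.9 with 20% versus 12%. These figures rest on independence and on all of the assumed worsening being recorded as infection.

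A reader might go further and infer that every serious COVID-19 deterioration, relapse or COVID-19 death becomes an infection AESI. The documents do not support that: entry depends on the diagnosis recorded and on MedDRA queries that are not named. Nor do they show that a signal will be hidden; the direction depends on the drug's effect on COVID-19. I would treat this as a cheap improvement.

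**What to change.** Leave the AESI definition in Protocol 9.3.4.1, the 24-hour reporting in 9.3.7.2 and the existing combined row as they are. Narrowing the definition would alter which nonserious events are reported quickly, and the analysis does not need that.

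In SAP 15.2.3 add two supplementary rows by arm:
- (a) participants with a Grade 3 or higher, serious or opportunistic infection other than COVID-19/SARS-CoV-2;
- (b) participants with a COVID-19 infection event.

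Assign events by a preferred-term list fixed blinded at the data review meeting before database lock, using the infecting agent where it is recorded. Assign relapses by pathogen, not by label: the relapse definition (Protocol 4.8, 9.1.3.2) accepts other respiratory pathogens, so a relapse can be a new infection. Show events with no identified agent separately; recording of the agent is asked for explicitly only at relapse. Use the same rows in any remaining IDMC outputs. SAP 6.1 and 6.2 describe meetings already held, and the output list they rely on is not among the documents, so it may already make this split.

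The cost is SAP wording, a short blinded term review and extra table rows. Some events may stay unclassified.
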